#### STUDY OBJECTIVE

Given the damaging effect of prolonged undetected hyperglycemia, prevention and early diagnosis of T2D is cost-saving and of public health importance. This research study is being done to assess if using a glucose sensor (also known as a continuous glucose monitor or CGM) after childbirth can help identify women who are at risk of developing diabetes after having diabetes during pregnancy or gestational diabetes. Currently, screening for diabetes after childbirth is performed with an oral glucose tolerance test 4-16 weeks after delivery, but this is burdensome and most patients are non-compliant. This study will use a CGM worn on the skin for 10 days. The data from the sensor will be compared to the standard oral glucose tolerance test as well as a HbA1c and fructosamine test. This is a single site study from patients with recent GDM that attended the diabetes clinic at Woman's Hospital. The research team plans to enroll 50 participants aged 18 years or older into the study. Participation in the study is expected to last up to 10 days during the postpartum interval. Study procedures include; 1) consent and screening; and 2) sensor placement and download after 10 days of wear postpartum during which an OGTT, fructosamine and HbA1c test will be administered.

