#### HbA1c, Fructosamine and OGTT data

We will use the glucose levels and HbA1c values as defined by the American Diabetes Association (ADA) guidelines(8) for the diagnosis of normal, prediabetes, and type 2 diabetes. Following the guidelines of ADA, a fasting blood glucose (FBG) below 126 or 2-h blood glucose (2hBG) < 140 mg/dl is considered normal glucose tolerance; FBG of 100-125 mg/dl or 2-h blood glucose (2hBG)  $\geq$  140- 199 mg/dl is classified as prediabetes, and FBG above or equal to 126 mg/dL or 2-h blood glucose (2hBG)  $\geq$  200 mg/dl in a standard oral glucose tolerance test (OGTT) as diabetic. The reference ranges for HbA1c results are:

- No diabetes: below 5.7%
- Borderline/prediabetes: 5.7% to 6.4%
- Diabetes: 6.5% or higher (8)

Fructosamine results may be considered alongside the HbA1c and other tests.

- In non-diabetics with normal albumin, fructosamine levels normally range between 175-265umol/L (micromoles per liter). For people with uncontrolled diabetes, the fructosamine range is 268-870 millimoles per liter (mmol/L). The concentrations of fructosamine corresponding prediabetes and diabetes clinical cut-points of 5.7% and 6.5% for HbA1c, based on percentiles, were 241.4 umol/L (the 77.1 percentile) and 270.2 umol/L (the 96.5 percentile), respectively (36).

Collection of glucose data The blinded glucose monitoring data on glycemia will be retrospectively assessed. The participant data collected from the CGM (Dexcom G7) will be downloaded with the Dexcom G7 reader and uploaded to Dexcom CLARITY

The percentage of time-in-target range, time hypoglycemia, and time hyperglycemia will be reported as either means with standard deviations (SD) or medians with interquartile ranges (IQR), depending on variable distribution. For analyses assessing overnight glycemia, daytime is defined as 5:00 AM to 11:59 PM and nighttime as 12:00 midnight to 4:59 AM

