#### Statistical analysis

Statistical analyses will be performed using SPSS version 15.1 for Windows (SPSS, Inc.; Chicago, IL). Continuous variables will be tested for normality of distribution using the Kolmogorov-Smirnov test. When necessary, non-normally distributed data will be subjected to logarithmic or square-root transformation to obtain a normal distribution where necessary for subsequent analyses. Continuous parameters will be given as means  $\pm$  standard deviations or medians with interquartile ranges (IQR). Results will be presented as mean  $\pm$  standard deviation for normally distributed continuous variables and as medians, with the 25th and 75th IQR for non-normally distributed variables. Categorical data will be presented as percentage. Pearson correlation coefficient ( $r$ ) and the significance for it ( $p$ ) will be calculated between the variables. The chi square test will be used to compare categorical variables. Chi-square test will be used to test differences in percentage proportionality Student t tests will be used to compare normally distributed groups; otherwise, Mann-Whitney rank sum tests will be used. Multiple groups will be compared using Kruskal-Wallis one-way ANOVA with a Dunn's test for pairwise comparisons when appropriate. A two-sided P-value  $< 0.05$  is considered statistically significant.

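### The plan applies one 0.05 significance rule to an open-ended set of tests, with no primary CGM analysis and no error control across metrics, time windows and comparators

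*Combined protocol and SAP*

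**What the plan says.** The Statistical analysis section is the whole analysis plan. A Pearson coefficient and its p-value "will be calculated between the variables", with no list of pairs. Chi-square, t or Mann-Whitney, and Kruskal-Wallis tests follow, with Dunn's test for pairwise contrasts; no outcome or grouping is named for any of them. The section closes with one rule: "A two-sided P-value" below 0.05 "is considered statistically significant".

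The candidate variables come from elsewhere:

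- **CGM metrics.** Under HbA1c, Fructosamine and OGTT data: "The percentage of time-in-target range, time hypoglycemia, and time hyperglycemia will be reported" as means or medians. There are three metrics, and none is ranked first.
- **Time windows.** The same section states that for overnight analyses "daytime is defined as 5:00 AM to 11:59 PM and nighttime as 12:00 midnight to 4:59 AM".
- **Comparators.** STUDY OBJECTIVE says the sensor data will be "compared to the standard oral glucose tolerance test as well as a HbA1c and fructosamine test". The OGTT classification uses a fasting and a 2-hour value, so there are four continuous reference values.
- **Sample size.** "The research team plans to enroll 50 participants aged 18 years or older into the study". No power, effect size or precision target accompanies the figure.

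No section of the supplied text names a primary analysis, an order of testing or an adjustment across these variables.

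**The concern.** The study asks whether CGM worn after delivery can help identify women at risk of diabetes. With no primary analysis, any metric, in any window, against any reference value, can supply a result that the plan itself calls statistically significant. A reader of the eventual report could not tell a planned finding from the best of many. The bar for each single test is also low. With 50 women, a correlation of about 0.28, which explains about 8% of the variance, crosses 0.05. A correlation of that size chosen after the fact would say little about whether CGM can screen.

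**Working it through.** **Plan's own figure.** The only design figure is 50 participants. It cannot be reproduced, because the plan states no power, effect size, SD, precision target, test count or overall error rate.

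**Inputs.** Two-sided 0.05 per test and n = 50 are from the plan. The counts below are assumptions, because the plan lists variables but not tests.

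- Smaller family: 3 metrics × 4 reference values (fasting glucose, 2-hour glucose, HbA1c, fructosamine) = 12 correlations.
- Larger family: 3 metrics × 3 windows (full wear, day, night) × 4 reference values = 36 correlations.

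**Step 1: independent tests, no real association.** The chance of at least one false positive among m tests is 1 − 0.95^m, and the expected number is 0.05m.

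- m = 12: 1 − 0.95^12 = 46.0%; expected 0.6.
- m = 36: 1 − 0.95^36 = 84.2%; expected 1.8.
- The chance first passes 50% at m = 14 (51.2%; m = 13 gives 48.7%).

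**Step 2: allowing for dependence.** CGM metrics are correlated with one another, and so are the reference values. The documents give no correlations, so a range was simulated: n = 50, Pearson tests at two-sided 0.05, equal correlation (rho) within the CGM set and within the reference set, and none between the sets. There were 10,000 replicates, or 4,000 where group tests were added.

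| Assumed family | Tests | rho 0 | rho 0.5 | rho 0.8 |
|---|---|---|---|---|
| 3 metrics × 1 reference | 3 | 14.0% | 13.0% | 9.9% |
| 3 metrics × 4 references | 12 | 45.8% | 35.5% | 21.5% |
| as above, plus one OGTT-group t test per metric | 15 | 52.2% | 39.7% | 24.3% |
| 6 CGM variables × 4 references | 24 | 71.3% | 54.1% | 29.7% |
| 9 CGM variables × 4 references | 36 | 84.0% | 65.4% | 34.8% |
| as above, plus one OGTT-group t test per variable | 45 | 87.5% | 70.4% | 40.9% |

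**Step 3: a smaller effective family.** If the three time percentages partition the wear time, they sum to 100% and only two are free. Then 2 × 4 = 8 tests give 1 − 0.95^8 = 33.7% if independent, and about 17% to 35% in simulation across the correlation range.

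**Step 4: what one test needs.** With n = 50 there are 48 degrees of freedom, and the critical |r| is t/√(48 + t²) = 0.279; 0.279² is about 0.078. Bonferroni over 12 tests (0.05/12 = 0.00417) raises the critical |r| to 0.398. Over 36 tests (0.05/36 = 0.00139) it is 0.440. One pre-specified test keeps the error rate at 0.05 with no such penalty.

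**The case against.** The case on the other side has several parts.

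- **The test count is not the plan's.** The three metrics are to be reported descriptively, and day and night are defined only for overnight analyses. Nothing says each metric in each window meets each comparator. This stands, so the counts are labelled as assumptions and both families are shown. Daytime covers 19 of 24 hours, so the full-wear and daytime metrics would be close to duplicates; this argues against treating the 36 tests as independent.
- **A reader might infer that at least one false positive is more likely than not.** The documents do not support that. It needs at least 14 independent tests, or roughly 24 to 36 moderately correlated ones, and the plan fixes no number. For 12 correlations every simulated figure is below 50%.
- **A reader might infer that no test is protected at all, or that there is no comparator.** Both go too far. Dunn's test is a multiple-comparison procedure, although it acts only within one Kruskal-Wallis comparison. The OGTT is recognisably the reference: STUDY OBJECTIVE calls it the standard and Background calls it the recommended test. What is missing is a declared primary analysis against it.
- **No real association anywhere is implausible,** since CGM and the OGTT both measure glucose in the same women over the same period. This is fair. The percentages describe the decision rule when no association is real; they do not predict the study's result. If a weak association is real, the rule would label it significant without showing that CGM discriminates, so the label still does not answer the study question.
- **The study is a small single-site observational cohort with no formal success criterion.** True, but the plan does not call its tests exploratory, and it attaches the significance label to all of them.

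**Conclusion.** The concern holds in limited form. The plan applies a two-sided 0.05 significance rule to an unlisted set of correlations and group tests. It has no primary CGM analysis and no error control across metrics, windows and comparators. The chance of at least one false positive when no association is real is about 22% to 46% if 12 tests are run and about 35% to 84% if 36 are run. Even three metrics against a single reference value give 9.9% or more, about twice the nominal 5%. These figures rest on assumed test counts, an assumed within-set correlation of 0 to 0.8, and complete data on 50 women. They show that the risk is uncontrolled; they do not show that a false positive is to be expected. This is a cheap improvement to the plan.

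**What to change.** In the Statistical analysis section:

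1. Name one primary analysis: one full-wear CGM metric already listed in the protocol, against OGTT-defined dysglycemia, by area under the ROC curve with a 95% CI. Percentage of time in hyperglycemia is one example. The sponsor should fix its threshold before the CGM data are unmasked. The 2-hour post-load OGTT cut-off is not by itself a CGM threshold. The choice of metric is the sponsor's; what matters is that it is made in advance.
2. Apply the 0.05 rule to that analysis only.
3. Report all other correlations and group tests as exploratory, with estimates and 95% CIs and no significance label.

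One step must come first. Under HbA1c, Fructosamine and OGTT data, a fasting value below 126 mg/dL counts as normal, while 100 to 125 mg/dL counts as prediabetes, so a value of 110 falls in both. The fasting and 2-hour criteria for normal are also joined by an or, so a woman could meet one category on one value and another on the other. These statements must be reconciled before the OGTT outcome is defined.

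The analysis is feasible. Background gives 30% persistent dysglycemia after GDM, and 0.30 × 50 = 15 expected cases if every woman completes the OGTT. With so few cases, the confidence interval should carry the interpretation.

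The cost is one paragraph of analysis text plus the clarified OGTT categories, with no new data. The downside is that secondary results can no longer be called statistically significant.
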